6.7 Study Calendar of Procedures

0.7 Study Calcidat of Frocedures									
	Pre-Study	Surgery	POD0- 2 hrs post-op	POD1	Week 1	Week 2			
Informed Consent	X								
Demographics	X								
Medical History	X					X			
Physical/Pelvic Exam	X	X				X			
PVR	X								
1 st backfill versus autofill void trial with PVR			X						
2 nd backfill void trial with PVR, if 1 st trial failed				X					
3 rd backfill void trial with PVR, if 2 nd trial failed					X				
IIQ-7 Questionnaire	X					X			
PPBC Questionnaire	X					X			
Satisfaction Survey						X			

# **6.8 Laboratory Procedures**

No samples will be sent to the laboratory within the study.

#### 7.0 STATISTICAL PLAN

## 7.1 Sample Size Determination

Due to the wide variety of incidence of voiding dysfunction found in the literature, a review of

our own cohort of patients was used to determine the sample size. From May of 2016 to April of 2017, 355 total laparoscopic benign hysterectomies were performed by the minimally invasive gynecology division. Of these, 182 had an autofill void trial and 173 had a backfill void trial. About 28.3% of the backfill void trial patients failed and went home with a catheter while 4.9% of the autofill void trial patients failed and went home with a catheter. Hence, using a 2-indendent group dichotomous power analysis with a power of 80% and a one-sided confidence interval of 95%, we will require 76 patients to be enrolled (38 patients per group). A mid-study analysis will be performed when ½ of the patients are enrolled. To account for patient dropout. We will be enrolling 10% more patients totaling 84 patients for the study.

#### 7.2 Statistical Methods

After all data has been collected, demographic information will be compared between the two groups in order to ensure that they are similar in age, BMI, race distribution, etc. These are all assumed to be of a Gaussian distribution hence the Student's t-test will be used to compare continuous values and the Chi-Square test will be used to compare categorical values. The proportion of urinary retention will be compared using a Chi-Square test and the results from the questionnaires will also be compared, likely using a Chi-Square test for categorical values and a Wilcoxon Rank Sum test for continuous variables since the results will likely not fit a Gaussian distribution.

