#### 2.0 STUDY OBJECTIVES

## 2.1 Primary Objective

The primary objective is to compare the rate of void trial failure after TLH with the backfill technique versus the autofill technique.

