## 2.2 Secondary Objectives

The following variables will also be compared between participants undergoing backfill void trial and autofill void trial:

- Time to discharge: time from arrival to post-anesthesia care unit (PACU) to time of discharge
- Incidence of urinary retention after discharge from hospital
- Incidence of UTI in the first 2 weeks after surgery
- Participants' short term quality of life during the first 2 weeks after surgery
- Participants' satisfaction with the void trials

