## 3.2 Primary Study Endpoints

The primary endpoint of this study will be to determine if the rate of void trial failure after TLH is different after the autofill method versus the backfill method.

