## 3.3 Secondary Study Endpoints

The following study endpoints will also be compared between participants undergoing backfill void trial and autofill void trial:

- The time to discharge will be measured for each participant. This will be determined by calculating the time between arrival to the PACU and the time of discharge using documentation from Epic and from the case report forms (CRFs).
- After discharge, participants will be monitored for any encounters for urinary retention (in our hospital system) and will be asked at their 10-14 day post-operative visit if they had a Foley catheter placed outside the hospital. Additionally, any participant who fails their 2nd void trial will be noted. The incidence of urinary retention post-discharge will be determined using this data.
- Any participant diagnosed with a culture-proven UTI will be noted.
- The IIQ-7 will be used to determine if there are any changes to the participants' short term quality of life before and after surgery.
- The PPBC will be used to determine if there are any changes to the participants' perception of bladder function before and after surgery.

- Participant satisfaction level with the method of void trial will be collected at the 10-14 day post-operative visit and compared between the two methods of void trial.

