measurer. The PVR will be measured using a bladder scanner. If the PVR is greater than 100 mL or if the patient is unable to void within the hour, the void trial will be considered "failed" and a Foley catheter will be replaced. Patients who randomize to the autofill void trial will be given a 500 cc bolus of crystalloid by the anesthesia team prior to leaving the operating room. These participants will be allowed to urinate at any time within the first 3 hours after surgery. The amount urinated will be recorded using a commode specimen collection measurer. The PVR will be measured using a bladder scanner. If the PVR is greater than 100 mL, the void trial will be considered "failed" and a Foley catheter will be replaced. We anticipate that most of these patients will void spontaneously within 2 hours of arrival to the PACU. At two hours postoperatively, any patient who cannot void or does not have the urge to void will have a bladder scan. If the patient has more than 300 cc in the bladder, she will be allowed 1 more hour to void. If she cannot, a Foley catheter will be placed and she will be considered to have failed the void trial. If the patient has less than 300 cc in the bladder, another 500 cc of crystalloid bolus will be given and we will await void for another hour. At 3 hours post-operatively, these patients will undergo another bladder scan. Those with greater than 300 cc of urine in the bladder will receive a Foley catheter. Those with less than 300 cc of urine in the bladder will have a backfill void trial by placing the remaining amount of fluid into the bladder for a total volume of 300 cc. The rest of the void trial will be completed as per normal backfill void trial protocol. The participants who have a replaced Foley catheter will receive education regarding usage of a leg bag and will be discharged home to return to the office the following business day where a repeat void trial will be performed using the backfill method as previously outlined. If participants are unable to be discharged home, they will be admitted overnight in the hospital with documented rationale. A backfill void trial will then be performed the following day. If participants fail the 2nd void trial, a Foley catheter will be replaced and will remain in place for 1 week, at which time a backfill void trial will be repeated once again in the office. If this void trial is failed as well, participants will be educated about and asked to perform self-catheterization at home and will follow up with Urogynecology.

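### Does Section 7.2 test the wrong outcome by naming urinary retention and not void trial failure?

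*Combined protocol and SAP*

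**What the plan says.** Section 2.1 sets the primary objective: to "compare the rate of void trial failure after TLH with the backfill technique versus the autofill technique". Section 3.2 makes the primary endpoint an answer to the same question, to "determine if the rate of void trial failure after TLH is different after the autofill method versus the backfill method".

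Section 7.2 names tests for demographics, one clinical proportion and the questionnaires. The clinical sentence is "The proportion of urinary retention will be compared using a Chi-Square test". It gives no time point and no definition.

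The word retention also appears in the secondary outcomes, each time with a qualifier. Section 2.2 lists "Incidence of urinary retention after discharge from hospital". Section 3.3 builds that endpoint from retention encounters in the hospital system, catheters placed elsewhere and failure of the second void trial, and ends "The incidence of urinary retention post-discharge will be determined using this data".

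Section 7.1 takes its planning rates from a 2016-2017 cohort: about 28.3% failure with backfill, and "4.9% of the autofill void trial patients failed and went home with a catheter". It asks for 38 per group with 80% power and a one-sided 95% confidence level.

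Section 5.4 defines failure by the residual volume or inability to void. For autofill women who have not voided by three hours it adds "Those with less than 300 cc of urine in the bladder will have a backfill void trial" and "The rest of the void trial will be completed as per normal backfill void trial protocol". Section 6.4 calls the post-hysterectomy trial the first void trial, and the calendar in 6.7 agrees.

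**The concern.** Read literally, the methods section never ties a test to the primary endpoint. The term it uses is close to the name of a secondary endpoint that selects different women. A woman who fails on the day of surgery and passes the next day is a primary failure but, absent another event, not a post-discharge retention case. A woman who passes and later returns in retention is the reverse.

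Two further points seem to add to the doubt. Section 7.1 speaks of failing and going home with a catheter, which would leave out a woman who fails and is admitted. Sections 2.1 and 3.2 compare techniques, although an autofill woman topped up at three hours has had part of both, and 7.3 does not say that analysis is by assigned arm.

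At stake would be a test of an outcome for which the trial was not sized. Study personnel are not blinded to outcomes (5.8) and a mid-study analysis is planned (7.1), so a loose definition might be settled after data are seen.

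**Working it through.** **1. Which outcome is the trial sized on?** Inputs from 7.1: p1 = 0.283 (backfill), p2 = 0.049 (autofill), alpha 0.05 one-sided, power 80%. The pooled rate is (0.283 + 0.049)/2 = 0.166 and the difference is 0.234.

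n per group = [z_alpha × √(2 × 0.166 × 0.834) + 0.8416 × √(0.283 × 0.717 + 0.049 × 0.951)]² / 0.234²

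- One-sided (z = 1.645): (1.645 × 0.5262 + 0.8416 × 0.4995)² / 0.05476 = 30.2, so 31. With continuity correction, (n/4) × [1 + √(1 + 4/(n × 0.234))]² = 38.3, so 39.
- Two-sided (z = 1.960), uncorrected: 38.5, so 39.

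The plan's 38 per group (76) is within one woman per group of either version. The sample size therefore belongs to void trial failure.

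**2. Power for that outcome.** Exact binomial enumeration of the uncorrected chi-square test, 38 per group, 28.3% versus 4.9%: 0.900 one-sided with backfill higher, 0.838 two-sided.

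**3. What the other reading would cost.** Suppose a share q of first-trial failures also meets the 3.3 definition, and a share s of women who passed develops retention later. Rate = q × failure rate + s × (1 − failure rate). The documents give neither q nor s, and q is taken as equal in both arms. One-sided power, 38 per group:

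| | q = 20% | q = 40% | q = 60% |
|---|---|---|---|
| s = 0 | 0.267 | 0.560 | 0.721 |
| s = 2% | 0.220 | 0.441 | 0.611 |
| s = 5% | 0.158 | 0.319 | 0.491 |

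For example, q = 20% and s = 0 gives 0.20 × 28.3% = 5.7% versus 0.20 × 4.9% = 1.0%. So the two outcomes are not interchangeable, and it matters which one 7.2 means.

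**4. Which one does 7.2 mean?**

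- The secondary endpoint is qualified as post-discharge in both 2.2 and 3.3. Section 7.2 uses the bare term.
- Section 1.3 reports a cited study that defined urinary retention as no void by 6 hours or a residual above 100 cc. This trial's rule in 5.4 is a residual above 100 mL or, in the backfill arm, no void within the hour. The protocol's own literature thus uses the bare term for something very like void trial failure.
- A methods section that tests one clinical proportion, in a trial with one primary proportion, is most naturally testing that one.

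**5. Is the outcome itself defined?** Section 6.4 identifies the first trial. Section 5.4 treats the top-up as a continuation of the same trial, scored under backfill rules, and its failure rule does not depend on whether the woman goes home. The 7.1 phrase describes a past cohort and not this trial's endpoint. Groups are formed by randomisation (5.3), and the top-up is part of the autofill pathway, so comparison by assigned arm is the ordinary reading.

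**6. Sensitivity to the top-up rule.** If the 4.9% did not count top-ups and topped-up women fail at 28.3%, the autofill rate is (1 − r) × 4.9% + r × 28.3%, which is 6.1%, 7.2% and 8.4% at assumed shares r of 5%, 10% and 15%. Power is 0.853, 0.802 and 0.745 one-sided, and 0.774, 0.707 and 0.637 two-sided. This is a planning uncertainty about the cohort rate. It does not depend on the label in 7.2.

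**The case for a change.** The best case for a change is that a statistical section should name its primary comparison in the endpoint's own words. Here it does not, the nearest named endpoint is a different one, personnel are unblinded, and the remedy is a sentence or two. The textual part of this stands: 7.2 never uses the 3.2 term, and someone reading it in isolation could go astray.

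The rest is weaker. The low-power figures need an analyst to add a qualifier that 7.2 lacks and to pass over 2.1, 3.2 and 7.1. A switch of definition after seeing data would contradict a primary endpoint already written in 3.2, and 8.5 gives the interim look a safety purpose. Either reading leads to a chi-square test, so no method is in dispute. A sensitivity analysis counting topped-up women as failures could misclassify underfilled bladders.

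One small gap is real. Autofill women above 300 cc at the three-hour scan after the second bolus receive a catheter under 5.4, but that sentence does not call it a failure. The parallel branch, for women above 300 cc at two hours who still cannot void, does. An analyst would score both groups alike.

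Reassurance about power has limits too. The 90% holds for a one-sided test with backfill higher. The hypothesis in 1.5 runs the other way, and one-sided power in that direction at the 7.1 rates is essentially zero. Section 7.2 states no sidedness. These are separate matters from the outcome label.

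**Conclusion.** The concern is right about the wording but needs no change to the plan. Section 7.2 uses a loose synonym for an outcome that 2.1, 3.2, 5.4, 6.4, 6.7 and 7.1 together identify: failure of the first, day-of-surgery void trial, by assigned arm, with top-ups scored by their result. Writing that out would leave the chi-square test, the 76 women and the expected result as they are, with exact power of 90% one-sided (backfill higher) or 84% two-sided at the planning rates. The 16% to 72% range for post-discharge retention depends on assumed values of q and s and on the less natural reading. The conclusion assumes that the 3.2 endpoint governs the primary analysis and that women are compared in the arm to which they were randomised.

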### 4.3 Subject Recruitment and Screening

Patients will be recruited from the Cleveland Clinic Florida Department of Gynecology, primarily from two providers' patients—[name] and [name]. These physicians will see and book patients for TLH as normally in the office. All patients scheduled for TLH will be offered enrollment in the study per the aforementioned inclusion and exclusion criteria. Enrollment will occur at the pre-operative consultation or by telephone prior to day or surgery. A brief description will be provided including the risks/benefits of enrolling in the study. An opportunity for questions will be provided. Patients who do not wish to participate in the study will not be enrolled. On the day of the surgery, in a private area of the pre-operative suite, a member of the research team will discuss the study with the patient to readdress the protocol and answer any new questions. An approved informed consent document will be signed at the pre-operative consultation if the patient is agreeable to participation. If the patient is enrolled by telephone, the informed consent document will be signed the morning of surgery.

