#### **6.0 STUDY PROCEDURES**

# 6.1 Pre-registration and Screening

All patients scheduled for TLH will be offered enrollment in the study per the above inclusion and exclusion criteria. Eligibility will be confirmed at this time by a member of the research team through patient interview and review of the available electronic health record. All enrolled participants will have a PVR checked and recorded in the clinic using the bladder scanner that is available to us or straight catheterization. The enrolled participants will also be asked to complete the Patient Perception of Bladder Condition (PPBC) and the Incontinence Impact Questionnaire-Short Form (IIQ-7) and the completed forms will be collected by the research team (see attached "Preoperative participant questionnaire"). 9,10

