## 6.6 Post-op Week 2 Visit

At the post-operative visit 10-14 days after the surgery, the participants will be evaluated and examined in the office. They will be asked to complete a questionnaire which includes the IIQ-7, the PPBC, and a void trial satisfaction question (see attached "post-operative participant questionnaire"). Participants will also be asked if they obtained a Foley catheter outside of the hospital at any urgent care centers, other doctors' offices, or emergency rooms. Additionally, participants will be asked if they have any urinary problems including dysuria, hematuria, frequency, hesitancy, urgency, or incomplete emptying. If any urinary complaints exist, participants will be asked to provide a urine sample for testing by urinalysis and urine culture. Participants will be treated per physician preference. After treatment, participation in the study will be considered completed.

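### Section 7.2 names only two-sample tests for PPBC and IIQ-7, states no use of their baselines, and could send a presumably graded PPBC to a Chi-Square test that ignores order

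*Combined protocol and SAP*

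**What the plan says.** - **Collection.** Sections 3.1 and 6.1 have enrolled participants complete the PPBC and IIQ-7 pre-operatively. At the 10-14 day visit (6.6), "They will be asked to complete a questionnaire which includes the IIQ-7, the PPBC, and a void trial satisfaction question". The calendar in 6.7 shows the same two time points for both instruments, and satisfaction at week 2 only.
- **Endpoints.** Section 3.3 introduces its list as comparisons between the two arms. Within it, "The IIQ-7 will be used to determine if there are any changes" in short-term quality of life before and after surgery, and "The PPBC will be used to determine if there are any changes" in perceived bladder function over the same interval.
- **Objective.** Section 2.2 lists quality of life in the first two weeks after surgery, which reads as a post-operative level. It has no entry for perception of bladder condition.
- **Analysis.** Section 7.2 compares the questionnaire results, "likely using a Chi-Square test for categorical values and a Wilcoxon Rank Sum test for continuous variables". It names no change score, baseline term or model, and assigns no instrument to either test.
- **Format.** The title of reference 10 describes the PPBC as a single-item measure. The number of answer levels is not given. The questionnaires are attachments and are not reproduced.

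**The concern.** The question in 3.3 is change compared between arms, and 7.2 does not define the analysis that would answer it. Two consequences follow.

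First, a single-item scale is the instrument most likely to be handled as categorical. An ordinary Chi-Square test treats graded answers as unordered labels. It spreads its sensitivity over every possible pattern of difference, including patterns nobody expects, and so loses power against a plain shift toward better or worse.

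Second, each participant's own pre-operative score is collected, but no use of it is stated. The choice between follow-up score, change and adjusted comparison is left open, and the test itself is only *likely*. Section 5.8 says study personnel are not blinded, so these choices could be made after results by arm are visible.

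At stake is the chance of detecting a real difference in bladder perception or quality of life with about 38 women per arm.

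**Working it through.** **Plan's own figure.** The documents give no power for the questionnaires, so there is none to reproduce. The only input taken from the plan is 38 per group (7.1). That figure reproduces from failure rates of 28.3% and 4.9% at 80% power, using n = [z_α√(2p̄q̄) + z_β√(p₁q₁ + p₂q₂)]² / (p₁ − p₂)² with p̄ = 0.166:

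- Two-sided 5%: (1.96 × 0.526 + 0.842 × 0.4995)² / 0.234² = 38.5, so 39.
- One-sided 5%: 31, or 39 with a continuity correction.
- Dropout: 76 × 1.10 = 83.6, so 84 as stated.

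Nothing below alters it.

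**Assumptions not in the documents.** Five or six ordered levels; a latent normal shift of 0.5-0.65 SD between arms; baseline to follow-up correlation ρ of 0.2-0.7; two-sided 5%.

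**Step 1: ordered item, 38 per arm, 4,000 simulated trials per case.** Power in %. The last two columns give ρ = 0.2 / 0.5 / 0.7.

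| Answer distribution (%) | Shift (SD) | Chi-Square, follow-up | Wilcoxon, follow-up | Wilcoxon, change | Rank ANCOVA |
|---|---|---|---|---|---|
| 20, 20, 20, 15, 15, 10 | 0.5 | 28-30 | 53-54 | 36 / 50 / 68 | 54 / 63 / 76 |
| same | 0.65 | 48-50 | 75-76 | 54 / 71 / 88 | 77 / 85 / 94 |
| 50, 20, 12, 8, 6, 4 | 0.5 | 25-26 | 49-51 | 35 / 47 / 64 | 52 / 57 / 69 |
| same | 0.65 | 43-48 | 73-74 | 56 / 71 / 86 | 74 / 81 / 90 |
| 10, 10, 20, 30, 30 | 0.5 | 29 | 50-51 | 29 / 41 / 57 | 51 / 59 / 71 |
| same | 0.65 | 47-48 | 71-73 | 44 / 58 / 75 | 74 / 80 / 89 |

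With no shift, Chi-Square rejected in 3.5-5.0% of trials and the rank methods in 4.3-5.6%, so all are acceptably calibrated.

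- Cost of ignoring order (Wilcoxon minus Chi-Square, same run): 21 to 30 points.
- Gain from baseline (rank ANCOVA minus Wilcoxon on follow-up): 0.5-2 points at ρ = 0.2, 8-10 at 0.5, 16-23 at 0.7.

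**Step 2: score treated as continuous (a summed IIQ-7).** Relative to the follow-up score alone, the variance is 2(1 − ρ) for a change score and 1 − ρ² for ANCOVA. Power = Φ(δ / (SD × √(2/38)) − 1.96). For the follow-up score alone at δ = 0.5: Φ(0.5/0.2294 − 1.96) = Φ(0.22) = 59%.

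| ρ | Variance, change | Variance, ANCOVA | Power, change | Power, ANCOVA |
|---|---|---|---|---|
| 0.2 | 1.60 | 0.96 | 41% | 60% |
| 0.3 | 1.40 | 0.91 | 45% | 63% |
| 0.5 | 1.00 | 0.75 | 59% | 71% |
| 0.7 | 0.60 | 0.51 | 80% | 86% |

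At this shift ANCOVA gains 2, 4, 12 and 28 points over the follow-up score. A change score loses 18 and 13 points at ρ = 0.2 and 0.3.

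**Step 3: floor effect.** Section 4.2 excludes known incontinence or retention, so many baselines may sit at the best level. Six levels, 0.6 SD shift, 3,000 trials per case, 80% of baselines at the best level, ρ = 0.2 / 0.3 / 0.5 / 0.7:

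- Chi-Square: 37-38%.
- Wilcoxon on follow-up: 65-67%.
- Rank ANCOVA: 65 / 67 / 72 / 77%, a gain of about 1, 2, 5 and 12 points.
- Wilcoxon on change: 60 / 64 / 71 / 79%.

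The floor shrinks the baseline gain. It leaves the loss from ignoring order at 28-29 points.

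**The case against.** The strongest defence is that 7.2 excludes nothing. It names tests, not the quantity tested, and a rank-sum test on change scores would fit both 3.3 and 7.2. A two-sample test on the follow-up score is also valid in a randomised trial and would answer the quality-of-life objective as 2.2 words it. The endpoints are secondary, no power is claimed for them, and the wording is openly provisional. In women without known incontinence or retention, baseline may carry little information.

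Much of this stands. The named tests are valid, and the value of baseline depends on a correlation the documents do not give. It does not rescue the wording. Sections 2.2 and 3.3 point to different quantities and 7.2 chooses neither. The change-score reading can cost power at low correlation. The Chi-Square loss does not depend on baseline at all.

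A reader might go further in four ways that the documents do not support:

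- *That 7.2 rules out baseline.* It is silent.
- *That both instruments lose their order.* A summed IIQ-7 would fall under the Wilcoxon test.
- *That the satisfaction item is mishandled.* Its answer format is not visible.
- *That women enrolled by telephone, who sign consent on the morning of surgery (4.3), have questionnaire baselines that are missing or precede consent.* Sections 3.1 and 6.1 place only the residual-volume measurement in the clinic. The questionnaire sentence gives no place, and 4.3 has a research team member meet the patient in the pre-operative suite that day.

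**Conclusion.** The point holds as an unspecified analysis variable combined with a poor default test for an ordered item. If PPBC is graded and analysed by Chi-Square, the loss is about 20-30 power points against a rank test, across all the answer distributions and shifts tried. That size rests on assumed levels and shifts, but its direction does not depend on baseline correlation.

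The baseline part is conditional. Adjustment adds about 1-5 points when correlation is low, or when baselines are near the floor and correlation is at most 0.5. Without a floor it adds roughly 8-28 points at correlations of 0.5-0.7. It would be wrong to infer that omitting baseline certainly forfeits a large share of power. The case for adjusting is that it did about as well as or better than the follow-up score alone at every correlation examined. A change score can do clearly worse than the follow-up score at low correlation.

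No figure in the plan is wrong, and the primary endpoint and its sample size are unaffected. The change is worth making because it costs almost nothing.

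**What to change.** Replace the questionnaire sentence in 7.2 with a rule for each instrument:

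- **PPBC:** compare the 10-14 day answer between arms by a proportional-odds model or rank ANCOVA, with treatment and the participant's own baseline answer. Name one of the two in advance.
- **IIQ-7:** compare the 10-14 day score by rank ANCOVA, with treatment and the participant's own baseline score.
- **Satisfaction:** use the Wilcoxon rank-sum test if the answers are ordered.
- Delete *likely*.

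Align 2.2 and 3.3 so that both describe the same quantity. The cost is a few sentences and a few lines of analysis code, with no additional participants, visits or data.
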